19.9. Neuro-QoL scales

Neuro-QOL Item Bank v1.0 - Lower Extremity Function (Mobility) - Short Form

Lower Extremity Function (Mobility) - Short Form

Please respond to each question or statement by marking one box per row.

		Without any difficulty	With a little difficulty	With some	With much difficulty	Unable to do
NQMOB37	Are you able to get on and off the toilet?	5	4	3	2	
NQMOB30	Are you able to step up and down curbs?	5	4	3	2	1
NQMOB26	Are you able to get in and out of a car?	5	4	3	2	
NQMOB32	Are you able to get out of bed into a chair?	5	4	3	2	1
NOMOB25	Are you able to push open a heavy door?	5	4	3	2	
NQMOB33	Are you able to run errands and shop?	5	4	3	2	
NQMOB31	Are you able to get up off the floor from lying on your back without help?	5	4	3	2	
NQMOB28	Are you able to go for a walk of at least 15 minutes?	5	4	3	2	

©2008-2013 David Cella and the PROMIS Health Organization on behalf of the National Institute for Neurological Disorders and Stroke (NINDS). Used with permission.

English March 6, 2014 Page 1 of 1

Neuro-QOL Item Bank v1.0 – Upper Extremity Function (Fine Motor, ADL) – Short Form

Upper Extremity Function (Fine Motor, ADL) - Short Form

Please respond to each question or statement by marking one box per row.

on		Without any difficulty	With a little difficulty	With some difficulty	With much difficulty	Unable to do
NQUEX29	Are you able to turn a key in a lock?	5	4	3	2	
NQUEX20	Are you able to brush your teeth?	5	4	3	2	1
NQUEX44	Are you able to make a phone call using a touch tone key-pad?	5	4	3	2	1
NQUEX36	Are you able to pick up coins from a table top?	5	4	3	2	1
NQUEX30	Are you able to write with a pen or pencil?	5	4	3	2	1
NQUEX28	Are you able to open and close a zipper?	5	4	3		
NQUEX33	Are you able to wash and dry your body?	5	4	3	2	1
NQUEX37	Are you able to shampoo your hair?	5	4	3		

©2008-2013 David Cella and the PROMIS Health Organization on behalf of the National Institute for Neurological Disorders and Stroke (NINDS). Used with permission.

English March 6, 2014 Page 1 of 1

19.10. Fall Questionnaire

1.]	How many times in the last year have you:
	Fallen to the ground:
	Had near falls (this means you lose your balance but retain your upright position, for
	instance, by grabbing on to something):
	Stumble and catch yourself:
2. 1	Did you ever hurt yourself because of a fall?
0	No
0	Once
0	More than once
3. '	What kind of injuries have you suffered as a consequence of a fall?
0	None
0	A fracture (i.e. A hip):
0	Other wounds (i.e. Bruises, scrapes, cuts):
0	Loss of consciousness
0	Other (i.e. Internal bleeding, including the brain):
4. `	When you fall, where does this usually take place?
0	Outdoors
0	Indoors
0	Both
5. \	When you fall, at what time does this usually take place?
0	Any time of day
0	Daytime
0	Evening
0	Night time (after going to bed)

6. In which direction do you fall most often?
O Backwards
O Forwards
O Sideward right / left (circle the correct answer)
O All directions equally
7. What do you do to prevent falling?
O Nothing
O Avoid certain activities (give examples):
O The use of aids (i.e. cane, walker, holding on to a person, holding on to furniture):
O Other:
8. Do you experience a fear of falling?
O No
O Slightly
O Very much
9. Can you give an indication of your confidence in balance during daily activities on a scale of 0 up to 100 on the below mentioned scale? Zero means no confidence and 100 means full confidence in performing the activities?

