Monitor AE/Concomitant Medication		X	X	X	X	X	X	X	Xº
Fall diary	•							-	
Food Journal	Xp	Xq		Xp		Xp		X^p	

- ^a Does not need to be performed in subjects who had echocardiogram done in the last 12 months before screening.
- b Serum and Urine Pregnancy Tests to be performed on all females, unless there is documented evidence confirming they are not of childbearing potential.
- ^c The cardio-pulmonary exercise test (CPET) should occur in the morning after fasting for a minimum of 2 hours, with neither caffeine nor nicotine for at least 12 hours before testing. All tests should be done at approximately the same time and order for each visit. The CPET should always precede the FARS-Neuro evaluation at all visits.
- d For Clinician Rated CGI, only question 1 will be answered at Screening and Day 1
- ^e Only VAS (for Fatigue) will be performed at Screening and Day 1. VAS (for Improvement of FA Symptoms) will not be performed at Screening or Day 1.
- f Patient Global Impression of Change (PGI-C) to be performed Day 30 and onwards only. Not to be performed at Screening and Day 1.
- ^g Only questions 8 and 9 of the Fall Questionnaire will be answered over phone visits
- h At Screening and Day 330, height will be collected, and body mass index (BMI) will be calculated.
- Safety labs, Lipid Profile and ECG do not have to be repeated at Day 1 if the screening and Day 1 visit is within 7 days (or less) of each other.
- ^j Safety laboratory tests include chemistry, hematology, and coagulation.
- ^k Safety laboratory tests and lipid profile should be performed in a fasting state.
- ¹ Urine Pregnancy test to be performed by subject at home on the day of the EOT phone call (before the call and after the last dose).
- ^m The study drug for the first 4 weeks of dosing will be dispensed at the study sites. Study Drug for the subsequent dosing months may be shipped to the subject or site from a drug depot or site, depending on the dispensing schedule.
- ⁿ Site to perform drug accountability with subject on the EOT call. Subject to return unused study drug/bottles to the site.
- ^o Any AE ongoing at EOT will be followed to conclusion or until stabilized.
- ^p The Diet Coach will have an initial call and as needed with the subjects (or parents/ caregivers as applicable) to discuss food journal requirement.
- ^q The food journal has to be completed through end of month 1, and every 2 weeks prior to next onsite visit.

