7.4. Exploratory endpoints

To demonstrate the efficacy of RT001 on change from baseline at 11 months in clinical symptoms as measured by:

- 1. Modified Friedreich's Ataxia Scale (mFARS)
- 2. Fatigue Symptom Scale (items 2. 4. 7.9 of the total fatigue scale)
- 3. Clinician-rated Clinical Global Impression of Change (CGI-C)
- 4. Activities of daily living (ADL) elements of fatigue scale (items 5,6, 8, 10, and 11)
- 5. Patient Global Impression of Change (PGI-C)
- To evaluate the effects of RT001 on Visual Analogue Scale [VAS]
- To evaluate the effects of RT001 on speech measurements and Speech Assessment questionnaire
- To evaluate the effect of RT001 on T25FW
- To evaluate the effects of RT001 on FARS-Neuro
- To evaluate the effects of RT001 on FARS-ADL.

- To evaluate the effects of RT001 on SF-36
- To evaluate the effects of RT001 on the Neuro-QoL scales (Upper Extremity Function and Lower Extremity Function)
- To evaluate the effects of RT001 on the frequency of falls as reported in a fall diary and subject's fear of falling
- To evaluate the effects of RT001 on the Patient Global Impression of Change (PGI-C) Scale
- To evaluate the effects of RT001 on efficacy assessments after 4 months of treatment
- To evaluate the effects of RT001 on efficacy assessments after 8 months of treatment
- To evaluate the effects of RT001 on ejection fraction as reported in the Echocardiogram
- To evaluate the effects of RT001 on hypertrophy as reported in the Echocardiogram

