Subjects will self-administer orally 9 capsules daily for the first month with a meal: 3 capsules with breakfast, 3 capsules with lunch, and 3 capsules with dinner for the first month. After this initial period the dose will be reduced to 6 capsules daily with a meal: 3 capsules with breakfast, and 3 capsules with dinner for the remainder of the trial, while on study drug. If a subject is unable to tolerate study drug because of adverse events during the initial loading period, the dose may be reduced to six capsules daily (5.76 g total dose) given as 3 capsules with breakfast, and 3 capsules with dinner. If a subject is unable to tolerate study drug because of adverse events after the dose reduction to six capsules daily (5.76 g total dose), the dose may be spread over three meals (2 capsules at breakfast, 2 capsules with lunch, and 2 capsules with dinner). If the subject is still unable to tolerate study drug after spreading it over three meals, the total dose may be reduced by 1-2 capsules/day, preferably by reducing the dose for a meal from 2 to 1 capsule(s) as needed. After 2 weeks of taking a dose of less than 6 caps/day, the subject should try to increase the dose to 6 capsules/day given as 2 capsules TID given with meals. If 6 caps/day is not tolerable, the subject can take the drug at the dose of less than 6 caps/day that was tolerable. The last dose of study drug will be taken at 4 weeks from Day 330 visit.

Participation is anticipated to require 13 months.

- Screening: Up to 30 days from start of treatment
- Treatment Period: treatment for a 12-month period

Safety assessments include physical and neurologic examinations, vital signs, 12-lead electrocardiogram (ECG) tracing, and clinical laboratory tests (hematology, clinical chemistry,

lipid profile, coagulation, and urinalysis) to identify adverse events (AEs). Adverse events will be evaluated for incidence, severity, and relationship to study drug.

The first dose of the study drug will be taken on Day 1. Bioanalytical measurements will be performed to determine the concentration of D2-LA, deuterated arachidonic acid (D2-ARA), nondeuterated linoleic acid (H2-LA) and nondeuterated arachidonic acid (H2-ARA) in plasma and red blood cells. Blood samples will be collected at month 4 (Day 120 ± 30 days), at month 8 (Day 240 ± 30 days), and at month 11 (Day 330 ± 30 days). All samples are to be obtained prior to dosing and prior to breakfast.

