12. EFFICACY ENDPOINTS, SAFETY, PHARMACOKINETIC, AND OTHER ASSESSMENTS

12.1. Efficacy Endpoints

Efficacy endpoints include the following:

- Exercise testing using CPET (peak workload and VO₂MAX)
- T1MW and T25FW
- Speech measurement recording
- Clinician-rated Scales
 - o FARS-Neuro
 - Clinician-rated CGI
- Questionnaires and scales completed by the subject
 - o FARS-ADL
 - o SF-36
 - Patient Global Impression of Change (PGI-C)
 - o VAS
 - Fatigue scale
 - o Neuro-QoL scale (lower extremity function and upper extremity function)
 - o Fall Questionnaire
 - Speech Assessment Questionnaire
- Frequency of falls, near falls, and stumbles as reported in a fall diary

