12.6.7. Fall Questionnaire

The subject will complete a Fall questionnaire at Screening, on Day 1, Day 120 (\pm 30 days), Day 240 (\pm 30 days), and Day 330 (\pm 30 days). In between the clinic visits the subject will be contacted by phone by a study site staff member and asked to complete questions 8 and 9 of the fall questionnaire. This will be done after 30, 60, 90, 150, 180, 210, 270 and 300 days of dosing. All calls have a window of \pm 7 days. Refer to Section 19.10 for the specific items assessed.

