12.6.8. Fall Diary

The subjects will be asked to keep a daily log (diary) documenting falls, near-falls, stumbles, and fear of falling from screening until the end of treatment. Falls are defined as any event that results in unintentionally falling to the ground. Near-falls are defined as losing balance with no fall to the ground (e.g. hold on to something/somebody, or fall onto a chair, bed, or other soft landing). Stumbles are defined as losing balance momentarily with regaining of footing and no fall.

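### Question 1 of the Fall Questionnaire keeps a one-year look-back at every clinic visit, so about two thirds of the period counted at Day 120 and one third at Day 240 is before first dose; questions 2 and 3 have no time limit at all

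*Combined protocol and SAP*

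**What the plan says.** Section 12.1 names the "Fall Questionnaire" among the efficacy endpoints, as an entry separate from the diary-based frequency of falls. On timing, Section 12.6.7 states: "The subject will complete a Fall questionnaire at Screening, on Day 1, Day 120", and goes on to Days 240 and 330, with a window of 30 days either side of each post-baseline visit. The monthly calls are lighter. A footnote to the Schedule of Events reads: "Only questions 8 and 9 of the Fall Questionnaire will be answered over phone visits".

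The form itself is in Section 19.10. Question 1 opens with "How many times in the last year have you" and collects counts of falls to the ground, near falls and stumbles. Question 2 asks whether the subject was *ever* hurt in a fall (no, once, more than once). Question 3 asks what injuries falls have caused and gives no period. No follow-up version of the form is provided. Section 8.1 fixes the start of exposure: "The first dose of the study drug will be taken on Day 1".

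The falls objective in Section 7.4 uses other sources: "To evaluate the effects of RT001 on the frequency of falls as reported in a fall diary and subject's fear of falling". Section 12.6.8 describes the diary as a daily log kept from screening to the end of treatment.

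The two instruments define a near-fall differently. The questionnaire has "near falls (this means you lose your balance but retain your upright position". The diary's examples are "hold on to something/somebody, or fall onto a chair, bed, or other soft landing".

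**The concern.** An efficacy item should count events in the period it is meant to evaluate. A one-year recall asked 4 or 8 months after first dose mixes treated with untreated time, and successive answers count many of the same falls again. Effects after 4 and 8 months are stated exploratory objectives (Section 7.4), and Section 14.1 sends the change-from-baseline values of all exploratory endpoints to a repeated-measures model with continuous time.

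If question 1 is analysed that way, a constant effect that starts at once will look small at first and then seem to grow, only because the look-back fills up with treated days. A truthful answer to question 2 can stay the same or get worse, but never improve. Question 3, as written, has the same limitation.

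At stake is whether these items can say anything useful about treatment at 4 and 8 months. The form could also seem to disagree with the diary for reasons unrelated to the drug.

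**Working it through.** The documents give no fall rate, effect size or power for falls, so there is no plan figure to reproduce. The check is arithmetic on the recall window.

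**Inputs**
- Look-back of 365 days (Section 19.10, question 1).
- First dose on Day 1 (Section 8.1).
- Full form at Days 120, 240 and 330, each ±30 days (Section 12.6.7).

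**Share of the look-back before first dose**, at study day d: (365 − d)/365.

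| Visit | Nominal | Range over visit window |
|---|---|---|
| Day 120 | 245/365 = 67% | 59% (Day 150) to 75% (Day 90) |
| Day 240 | 125/365 = 34% | 26% (Day 270) to 42% (Day 210) |
| Day 330 | 35/365 = 10% | 1% (Day 360) to 18% (Day 300) |

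**Overlap.** The Day 120 look-back runs from day −245 to day 120, and the Day 240 look-back from day −125 to day 240. They share days −125 to 120, which is 245 of 365 days.

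**Attenuation.** Assume a constant underlying fall rate and a relative reduction E that is complete from Day 1. The reduction visible in question 1 is then E × d/365, so the visible fraction is 120/365 = 33%, 240/365 = 66% and 330/365 = 90%. No value of E is given in the documents; the following are illustrations.

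| Assumed true reduction | Seen at Day 120 | Seen at Day 240 | Seen at Day 330 |
|---|---|---|---|
| 30% | 10% | 20% | 27% |
| 40% | 13% | 26% | 36% |
| 50% | 16% | 33% | 45% |

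**Sensitivity to a gradual effect.** Suppose instead that the reduction grew linearly from zero to 40% at Day 330.
- Its mean over Days 0 to 330 is 20%, so question 1 at Day 330 shows 20% × 330/365 = 18%.
- A recall starting at Day 240 would average 40% × (240/330 + 1)/2 = 35%.

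The mild dilution at Day 330 in the tables therefore depends on the effect being immediate.

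**Near-falls side by side.** Losing balance and grabbing hold of something counts in both instruments. Dropping onto a chair or bed is a near-fall in the diary. On the questionnaire the subject has neither stayed upright nor reached the ground, so the event has no clear category. Falls to the ground are defined compatibly, and so are stumbles.

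**The case against.** The strongest reply is that the trial does not rely on this item for falls. A reader might infer from the look-back that any effect on falls will be diluted or missed. The documents do not support that. Sections 7.4 and 12.1 take fall frequency from the daily diary, which starts before dosing, is collected at Day 1 and at each later clinic visit, and has no one-year recall. Fear of falling (question 8) and balance confidence (question 9) ask about the present, and they are the only items used on the phone calls. This part of the reply stands in full.

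Three further points have force. Both randomised arms carry the same pre-dose share, so the between-arm comparison loses sensitivity but is not biased. At 11 months the nominal pre-dose share is only 10%. And no section names question 1, 2 or 3 as an analysed variable; Section 14.1 leaves detail to a separate plan.

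A reader might also conclude that the diary and the questionnaire cannot be compared at all. That goes too far: the conflict concerns near-falls with a soft landing.

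What remains is that the questionnaire is listed as an efficacy endpoint in its own right, is repeated in full at three treated visits, and is covered by the general rule for exploratory endpoints. Nothing says that questions 1 to 3 are history only, or which source prevails if the two disagree.

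**Conclusion.** The concern holds for questions 1 to 3 and goes no further. As written, question 1 counts a period that is 67% untreated at Day 120 (59–75% over the visit window), 34% at Day 240 (26–42%) and 10% at Day 330 (1–18%). These shares follow from the documents alone. The visible fractions of about 33%, 66% and 90% also assume a constant fall rate and an immediate effect; a gradual effect would be attenuated more, including at Day 330. Questions 2 and 3 cannot register on-treatment improvement at any visit.

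The consequence is a weak exploratory measure, chiefly at 4 and 8 months, together with near-fall counts that are not directly comparable with the diary. It is a loss of sensitivity within one form. It gives no reason to doubt the diary-based endpoint or the primary and secondary analyses.

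**What to change.** 1. Keep the one-year wording at both pre-dose visits, Screening and Day 1, as fall history. It adds something the diary cannot: with screening 14 to 30 days before first dose (Section 13.1), the diary's run-in is short.
2. At Days 120, 240 and 330, reword questions 1 to 3 to cover the time since the last clinic visit.
3. Report question 1 as events per 30 days, using actual visit dates. The visit windows let the Day 120 to Day 240 interval run from 60 days (Day 150 to Day 210) to 180 days (Day 90 to Day 270).
4. Compare arms on post-baseline rates, with the one-year history as a covariate, rather than on change from baseline. Baseline and follow-up would then have different recall lengths, and scaling to 30 days does not remove differences in recall accuracy.
5. Use one near-fall definition in both instruments.

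If the forms are already in use, the minimum is one sentence in the analysis plan: questions 1 to 3 are descriptive at baseline only, and post-baseline fall counts come from the diary.

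The cost is a revised follow-up form with its eCRF labels, and a flag for subjects who have already answered the old wording. The reworded question 1 will partly duplicate the diary, which is an argument for the one-sentence option if the sponsor prefers to leave the form alone.

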19.11. Speech Assessment Questionnaire

For subject:

How would you rate the overall quality of your speech?

Very Good	Good	Fair	Poor	Very Poor

How would you rate your verbal communication with your family or friends?

Very Good	Good	Fair	Poor	Very Poor

For parents, caregiver or travel companion response (not for patients to respond) Enter NA, if not present:

How would you rate the subject's overall quality of verbal communication?

Very Good	Good	Fair	Poor	Very Poor

19.12. Optional PK Profile Sub-Study: Pharmacokinetic Profile of RT001 at Steady State in Subjects with Friedreich's Ataxia Who Participated in Study RT001-006

19.12.1. Study Objectives

The objective of the study is to evaluate the pharmacokinetic (PK) profile of RT001 at steady state.

19.12.2. Study Design

At selected sites, subjects who are enrolled in RT001-006 will be invited to participate in this study. At the time of the Month 11 visit in RT001-006, PK samples will be obtained 30 minutes to 1 hour before the morning dose; and 30 min, 1, 2, 4, 8, 12 and 24 hours after the initial morning dose. It is recommended that the blood draws are done on a different day than the study procedures for the Month 11 visit in RT001-006.

19.12.3. Randomization

There will be no randomization. All subjects who are volunteering for this sub-study will be enrolled.

19.12.4. **Blinding**

Subjects and study personnel, including but not limited to investigators, study coordinators, nursing staff, clinical monitors, the Sponsor, and the Sponsor's representatives, will remain blinded to the study treatment assignments (RT001 or placebo) in RT001-006.

19.12.5. Inclusion Criteria

- 1. At selected sites, subjects who are enrolled in RT001-006 will be invited to participate in this study.
- 2. All participating subjects will be required to sign an informed consent prior to the collection of the blood draws.
- 3. Subjects must be willing to stay overnight close to the study site and able to provide the necessary repeated blood samples.

19.12.6. Sample Size

Subjects who are enrolled in RT001-006 will be invited to participate in this study. Because the study treatment (active or placebo) in RT001-006 is blinded, a minimum of 10 subjects will be enrolled to ensure that at least 5 subjects who are randomized to active are enrolled in this study. An unblinded person may be asked to verify that at least 5 of the selected subjects were randomized to active. Additional subjects may be added as needed.

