2. STUDY SYNOPSIS

Sponsor:	Retrotope, Inc. [name]
Title:	A Randomized, Double-Blind, Controlled, Phase 2/3 Study to Assess Efficacy, Long Term Safety and Tolerability of RT001 in Subjects with Friedreich's Ataxia
Protocol No:	RT001-006
Study Drugs:	Active : RT001, 960 mg soft gelatin capsules (9-cis, 12-cis-11,11-D ₂ -linoleic acid ethyl ester [deuterated ethyl linoleate, or D ₂ -LA])
	Placebo: Soft gelatin capsule of USP safflower oil (Placebo or H ₂ -LA)
Study Population:	Friedreich's ataxia (FRDA) patients who meet all entry criteria.
Number of Subjects	The planned enrollment is 60 subjects randomized 1:1 (active: placebo). Randomization will be stratified by Friedreich Ataxia Rating Scale (FARS) Neurological score: ≤45 and >45 Enrollment of patients with age > 25 will be capped at 25 % of the total enrollment
Dosing Schedule	Subjects will receive the content of nine capsules daily (8.64 g total dose) given as 3 capsules three times a day (TID) with meals for the first month of treatment. After this initial loading period, the dose will be reduced to six capsules daily (5.76 g total dose) given as 3 capsules with breakfast, and 3 capsules with dinner for the remainder of the trial, while on study drug. If a subject is unable to tolerate study drug because of adverse events during the initial loading period, the dose may be reduced to six capsules daily (5.76 g total dose) given as 3 capsules with breakfast, and 3 capsules with dinner. If a subject is unable to tolerate study drug because of adverse events after the dose reduction to six capsules daily (5.76 g total dose), the dose may be spread over three meals (2 capsules at breakfast, 2 capsules with lunch, and 2 capsules with dinner). If the subject is still unable to tolerate study drug after spreading it over three meals, the total dose may be reduced by 1-2 capsules/day, preferably by reducing the dose for a meal from 2 to 1 capsule(s) as needed. After 2 weeks of taking a dose of less
	than 6 caps/day, the subject should try to increase the dose to 6 capsules/day given as 2 capsules TID given with meals. If 6 caps/day is not tolerable, the subject can take the drug at the dose of less than 6 caps/day that was tolerable.
Route of Administration:	Oral
Study Centers:	up to 10 study centers
Phase of Development	Phase 2/3

Objectives

Primary endpoints:

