8.2. Randomization

The randomized, double-blind design of the study is intended to minimize bias on the part of subjects, investigators, and analysts. Subjects who meet all enrollment criteria and from whom consent has been obtained will be randomly assigned to receive one of two treatments (RT001 or placebo capsules) following a 1:1 ratio. Randomization will be stratified as much as possible according to the FARS Neurological score (baseline FARS score of \leq 45 and >45). Enrollment of patients with age > 25 will be capped at 25 % of the total enrollment.

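### Ten PK-profile volunteers give five active subjects on average, not with certainty, and the check that would reveal a shortfall is optional

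*Combined protocol and SAP*

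**What the plan says.** Section 19.12.6 sets the size of the optional PK profile sub-study. Because treatment in the main trial is blinded, "a minimum of 10 subjects will be enrolled to ensure that at least 5 subjects who are randomized to active are enrolled". Two further sentences follow: "An unblinded person may be asked to verify that at least 5 of the selected subjects were randomized to active", and "Additional subjects may be added as needed".

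On recruitment, section 19.12.3 states: "There will be no randomization. All subjects who are volunteering for this sub-study will be enrolled". Section 19.12.5 limits the source: "At selected sites, subjects who are enrolled in RT001-006 will be invited to participate in this study".

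The main trial plans 60 subjects allocated 1:1 (synopsis; section 8.1). Section 8.2 says: "Randomization will be stratified as much as possible according to the FARS Neurological score". It names no other stratification factor. Section 19.12.4 keeps sites, sponsor and sponsor's representatives blinded during the sub-study. The profile is taken immediately before or after the Day 330 visit (section 12.8.1), and study drug ends four weeks after that visit (section 11.1).

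**The concern.** The paragraph gives ten volunteers as a number that secures five on active treatment. With equal allocation and no selection by arm, ten secures that only on average. The two sentences that could repair a shortfall are both permissive. The text can therefore be followed to the letter and still end with fewer than five active subjects, without anyone on the study team knowing.

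What is at stake is limited but specific. The objective is the steady-state profile of RT001 (section 19.12.1), summarised by AUC, Cmax and Tmax (section 19.12.9). Subjects on placebo receive non-deuterated oil and contribute nothing to the D2-LA profile. Section 14.1 also promises minimum and maximum exposure at steady state, and the main trial's pre-dose samples cannot show a maximum.

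**Working it through.** **Inputs.** Minimum volunteers n = 10 and target of at least 5 active (section 19.12.6). Main trial 60 subjects at 1:1, so 30 active and 30 placebo (synopsis). No quota by arm (section 19.12.3). Let X be the number of active subjects among the volunteers. Assume at first that volunteering is unrelated to arm.

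**Step 1: where ten comes from.** Setting the expected number of active subjects to five gives n = 5 / 0.5 = 10. The plan's figure is recovered as an average, not as an assurance.

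**Step 2: binomial, n = 10, p = 0.5.**
P(X ≥ 5) = 1 − (1 + 10 + 45 + 120 + 210)/1024 = 1 − 386/1024 = 638/1024 = 0.623.

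**Step 3: hypergeometric, 10 drawn from 60 with 30 active.**
P(X = 5) = C(30,5)² / C(60,10) = 142,506² / 75,394,027,566 = 0.269. The distribution is symmetric about 5, so P(X ≥ 5) = (1 + 0.269)/2 = 0.635.

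The volunteers come from selected sites, and the size of that pool is not given. Assumed balanced pools of 40, 50 and 54 give 0.642, 0.637 and 0.636. The range across these models is 62% to 64%.

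**Step 4: if the active share among volunteers is not one half.** Site is not a named stratification factor, so balance within the selected sites is not assured. With assumed active shares of 0.40, 0.45, 0.55 and 0.60, the binomial chance of at least five in ten is 36.7%, 49.6%, 73.8% and 83.4%. None of these amounts to a guarantee.

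**Step 5: more than ten volunteers.** Chance of at least five active:

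| Volunteers | Binomial | Hypergeometric (30 of 60) |
|---|---|---|
| 10 | 0.623 | 0.635 |
| 12 | 0.806 | 0.833 |
| 14 | 0.910 | 0.937 |
| 15 | 0.941 | 0.964 |
| 16 | 0.962 | 0.981 |
| 18 | 0.985 | 0.995 |
| 20 | 0.994 | 0.999 |

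About 95% assurance needs 15 (hypergeometric) or 16 (binomial). A strict guarantee without looking at the codes needs 30 + 5 = 35 of 60, because the first 30 could all be on placebo.

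**Step 6: how large a shortfall would be.** At ten volunteers, P(X ≥ 4) is 0.83 (binomial) or 0.85 (hypergeometric), and P(X ≥ 3) is 0.95 or 0.96. Under the binomial, 210/386 = 54% of shortfalls are by one subject only.

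**Step 7: what else is sampled.** Main-trial PK samples at months 4, 8 and 11 are all pre-dose (section 12.8.1). Washout samples are taken 7 days and 4, 12 and 24 weeks after the last dose (section 13.11). Only the profile sub-study samples between one dose and the next (section 13.9).

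**The case against.** The strongest reply is that the remedy is already in the paragraph. The authors provide for a check and for extra subjects, and 'as needed' can sensibly mean only needed to reach five active. Ten is a floor, and all volunteers are taken, so the realised number may be well above ten. By 14 volunteers the chance of five active already exceeds 90%.

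Much of this stands. A reader might infer that the sub-study has a 37% chance of failing its target. The documents do not support that. The figure of 36% to 38% applies only at exactly ten volunteers with no top-up, and the documents do not say how many volunteers are expected. The actual risk is unknown.

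A reader might also infer that a shortfall would defeat the sub-study's objective. That is not supported either. The objective is descriptive, and no hypothesis, power or precision target is attached to five. Table 7 reports Day 28 parameters from the sponsor's earlier study on 6 and 5 subjects per cohort, and half-life on 4 in one of them.

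What the reply does not answer is the dependence between the two permissive sentences. A top-up can be recognised as needed only if someone has looked at the codes, and that look is optional. No time is set for it. If it comes after most subjects have passed Day 330, there may be few or none left to add.

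**Conclusion.** The point holds as a wording and procedure defect of minor weight. At the stated minimum of ten, the chance of at least five active subjects is about 62% to 64%, so the minimum does not do what the sentence says. This assumes exactly ten volunteers, no top-up, volunteering unrelated to arm, and an equal split in the pool they come from. The safeguards in the paragraph would close the gap if used in time, but nothing requires their use.

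Two further inferences go too far. The sub-study is not the only source of samples taken after dosing, because the washout sub-study also provides some. It is the only scheduled source within a dosing interval. Nor are placebo profiles without any use: H2-LA and H2-ARA are listed analytes (section 19.12.7), and placebo subjects contribute to those. They contribute no D2-LA profile. The sub-study is optional, and no efficacy or safety conclusion depends on it.

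**What to change.** In section 19.12.6:

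- Change 'may be asked' to 'will be asked'. Name an unblinded person outside the study team; section 15.7 already refers to an unblinded statistician or designee. That person reports only whether more subjects are needed.
- Set the check at a time when eligible subjects have yet to pass the Day 330 window.
- Require top-up until five active subjects have been sampled or the eligible volunteers run out. Add subjects in small groups rather than singly: if the answer changes from 'more needed' to 'enough' after one added subject, that subject is revealed as active.
- Replace 'to ensure' with wording such as 'so that on average 5'. Alternatively, raise the minimum to about 15 or 16, which gives roughly 95% assurance without relying on the check.

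The cost is a few edited sentences and possibly a few more volunteers, which the plan already permits. The check uses a mechanism that the paragraph already allows, and individual assignments stay undisclosed.
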